6.2 Pharmacodynamics

Analyses will be performed in the pharmacodynamic analysis set (see Section 7.2 Datasets for Analysis).

For each of the endpoints listed below, descriptive statistics (number of subjects, mean, standard deviation, minimum, median, and maximum) of the measurement and the change from baseline will be calculated for each group at each time point after the start of IMP administration. For daily urine volume, daily fluid intake, and daily fluid balance after IMP administration on Day 1 and after final IMP administration, the difference (each OPC-61815 injection group – tolvaptan 15-mg tablet) in mean change from baseline and its 95% confidence interval will be calculated.

- Serum sodium concentration, serum potassium concentration
- Serum osmolality
- Biomarkers (plasma BNP concentration, serum NT-proBNP concentration, serum troponin concentration, plasma AVP concentration, plasma renin activity)
- Daily urine volume
- Daily fluid intake
- Daily fluid balance
- Daily urine sodium excretion
- Daily urine potassium excretion
- Urine osmolality

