3.4 Handling of Time Points

CRF Visit values at each time point (run-in period, treatment period, and follow-up) will be used in summaries (but values at the time of discontinuation will not be used in summaries). Unscheduled Visit values will not be used.

Baseline and final administration time point for each variable are defined as follows.

Variable	Baseline ^a	Final Administration Time Point
Body weight	Before IMP administration on Day 1	Day after final IMP administration
Congestive symptoms	Run-in period (final measurement)	Day after final IMP administration
Pulmonary congestion, cardiothoracic ratio	Run-in period	Day after final IMP administration
NYHA classification	Run-in period	Day after final IMP administration
Clinical laboratory value	Before IMP administration on Day 1	Day after final IMP administration
Vital signs	Before IMP administration on Day 1	Day after final IMP administration
12-lead ECG	Run-in period	Day after final IMP administration
Serum sodium concentration, serum potassium concentration, serum osmolality, biomarker	Before IMP administration on Day 1	-
Daily urinary output, daily fluid intake, daily water balance, daily sodium urinary excretion, daily potassium urinary excretion, urinary osmolality	During 24 hours before start of IMP administration on Day 1	-

^aWhen multiple data are collected during the run-in period, the data closest to Day 1 will be used as baseline.

4 Sample Size

The primary objective of this clinical trial is to compare tolvaptan exposure in order to investigate the dose of OPC-61815 injection required to achieve exposure equivalent to tolvaptan 15-mg tablet for use in conducting phase 3 confirmatory clinical trials of OPC-61815. The number of subjects required for this purpose was determined to be at least 10 subjects per group (50 subjects in total) who complete blood sampling for measurement of plasma drug concentrations up until 24 hours postdose on Day 1. In consideration of the possibility of some subjects withdrawing from the trial prior to 24 hours postdose on Day 1, the approximate target number of subjects for the start of IMP administration is set at 11 subjects per group (55 subjects in total).

5 Statistical Analysis Sets

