8.1 Body Weight

Analysis of covariance using baseline weight as covariate will be performed on the change from baseline in body weight after final administration to calculate the least-square mean of the difference between each OPC-61815 injection group and tolvaptan 15-mg tablet group and its two-sided 95% confidence interval (based on the t

distribution). At each time point, descriptive statistics of measurement and change and percent change from baseline will be calculated for each group.

For changes in body weight from baseline, a timecourse (mean \pm standard deviation) from Day 1 of treatment period to follow-up will be created for each treatment group. For changes in body weight from baseline to the final IMP administration, a bar graph of least square means (two-sided 95% confidence interval) with the horizontal axis representing treatment groups will be created.

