8.2.2 Jugular Venous Distension, Hepatomegaly, and Cardiotoracic Ratio

Change from baseline in jugular venous distension and cardiotoracic ratio after final administration will be analyzed using analysis of covariance with baseline value as

covariate to calculate the least square mean of the difference between each OPC-61815 injection group and tolvaptan 15-mg tablet group and its two-sided 95% confidence intervals (based on the t distribution). Descriptive statistics of the measurements and their changes from baseline at each time point for jugular venous distension, hepatomegaly, and cardiothoracic ratio will be calculated for each group.

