11 Pharmacodynamic Analyses

Analyses will be performed in the pharmacodynamic analysis set.

For each of the endpoints listed below, descriptive statistics (number of subjects, mean, standard deviation, minimum, median, and maximum) of the measurement and the change from baseline will be calculated for each group at each time point. For daily urine volume, daily fluid intake, and daily fluid balance after IMP administration on Day 1 and after IMP administration on Day 5, the difference (each OPC-61815 injection group – tolvaptan 15-mg tablet) in mean change from baseline and its 95% confidence interval (based on t distribution) will be calculated.

For daily urine output, a transition chart of measurements (mean \pm standard deviation) from the run-in period to Day 5 will be created in each group. For changes from baseline after IMP administration on Day 1 and after IMP administration on Day 5, a bar graph of

the mean (two-sided 95% confidence interval) with the horizontal axis representing treatment groups will also be created.

- Serum sodium concentration, serum potassium concentration (at the central laboratory)
- Serum osmolality
- Biomarkers (plasma AVP concentration, plasma BNP concentration, plasma renin activity, serum NT-proBNP, serum troponin concentration)
- Daily urine volume
- Daily fluid intake
- Daily fluid balance
- Daily urine sodium excretion
- Daily urine potassium excretion
- Urine osmolality

12 Pharmacogenomic Analyses

No pharmacogenomic analysis will be performed in this trial.

13 Interim Analysis

No interim analysis will be performed in this trial.

14 Changes in the Planned Analyses

- For further clarification, handling of discontinued subjects and subjects with missing data was added to Protocol 6.1.1. Pharmacokinetic Analysis Set.
- For erroneous entry, “V” described in Protocol 6.1.2 (1) (b) Secondary endpoints 2 was changed to “V_z.” Since “V_z/BW” was erroneously omitted, it was added.
- For omission in entry, an explanatory note on treating C_{24h} as the plasma concentration for the calculation of descriptive statistics was added.
- For omission in entry, a note considering IMP administration methods in addition to the manual on data handling was added.
- In Protocol 6.1.2 (3) Analytical Method 2), the analysis set for primary endpoints was added for clarification.

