CT-12.3.3 Incidence of Categorical Changes in Electrocardiogram Results on Day 1 (Safety Analysis Set)

CT-12.3.4 Incidence of Categorical Changes in Electrocardiogram Results on Day 3 (Safety Analysis Set)

CT-12.3.5 Incidence of Categorical Changes in Electrocardiogram Results on Day 6 (Safety Analysis Set)

CT-12.3.6 Incidence of Categorical Changes in Electrocardiogram Results on Last Visit (Safety Analysis Set)

PDT-1 Descriptive Statistics for Serum Sodium Concentration (mEq/L) (Pharmacodynamics Analysis Set)

PDT-2 Descriptive Statistics for Serum Potassium Concentration (mEq/L) (Pharmacodynamics Analysis Set)

PDT-3 Descriptive Statistics for Serum Osmolality (mOsm/kg) (Pharmacodynamics Analysis Set)

PDT-4 Descriptive Statistics for Plasma BNP Concentration (pg/mL) (Pharmacodynamics Analysis Set)

PDT-5 Descriptive Statistics for Serum pro BNP Concentration (pg/mL) (Pharmacodynamics Analysis Set)

PDT-6 Descriptive Statistics for Serum Troponin Concentration (pg/mL) (Pharmacodynamics Analysis Set)

PDT-7 Descriptive Statistics for Plasma AVP Concentration (pg/mL) (Pharmacodynamics Analysis Set)

PDT-8 Descriptive Statistics for Plasma Renin Activity (ng/mL/hr) (Pharmacodynamics Analysis Set)

PDT-9 Descriptive Statistics for Daily Urine Volume (mL) (Pharmacodynamics Analysis Set)

PDT-10 Descriptive Statistics for Daily Fluid Intake (mL) (Pharmacodynamics Analysis Set)

PDT-11 Descriptive Statistics for Daily Fluid Balance (mL) (Pharmacodynamics Analysis Set)

PDT-12 Descriptive Statistics for Daily Urine Excretion of Sodium (mEq) (Pharmacodynamics Analysis Set)

PDT-13 Descriptive Statistics for Daily Urine Excretion of Potassium (mEq) (Pharmacodynamics Analysis Set)

PDT-14 Descriptive Statistics for Urine Osmolality (mOsm/kg) (Pharmacodynamics Analysis Set)

CF-1 Transition Diagram for Body Weight (Efficacy Analysis Set)

CF-2 Bar Graph for Body Weight (Efficacy Analysis Set)

CF-3 Scatter Plot for Clinical Laboratory Tests (Safety Analysis Set)

CF-4 Transition Diagram for Daily Urine Volume (Pharmacodynamics Analysis Set)

CF-5 Bar Graph for Daily Urine Volume (Pharmacodynamics Analysis Set)

PKT-1.1.1.1 Individual and Summary of OPC-61815 Plasma Concentration Following Single Intravenous Administration of OPC-61815

PKT-1.1.1.2 Individual and Summary of OPC-41061 Plasma Concentration Following Single Intravenous Administration of OPC-61815

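### Daily urine volume, fluid intake and fluid balance are compared by unadjusted mean change; adjusting for the 24-hour pre-dose baseline is an optional, low-cost gain in precision, not the correction of an error

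*SAP*

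**What the plan says.** SAP Section 11 compares each OPC-61815 group with the 15-mg tablet on three pharmacodynamic variables, on Day 1 and Day 5. The difference "in mean change from baseline and its 95% confidence interval (based on t distribution) will be calculated". Protocol Section 6.2 plans the same unadjusted contrast: the difference "in mean change from baseline and its 95% confidence interval will be calculated". The protocol's second time point was after final administration; SAP Section 14 records the change to Day 5. For urine volume, SAP Section 11 also plans a bar graph of "the mean (two-sided 95% confidence interval) with the horizontal axis representing treatment groups will also be created".

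SAP Section 3.4 gives all three variables the same baseline window: "During 24 hours before start of IMP administration on Day 1".

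Elsewhere the SAP does adjust for baseline. In Section 8.1, "Analysis of covariance using baseline weight as covariate will be performed on the change from baseline in body weight". In Section 8.2.2, "Change from baseline in jugular venous distension and cardiotoracic ratio after final administration will be analyzed using analysis of covariance".

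SAP Section 11 does not say whether the t interval takes its variance from the two arms compared or pools it over all five.

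**The concern.** A change score fixes the coefficient on baseline at 1. If the true slope is well away from 1, the change carries baseline noise that a fitted covariate would remove. The baseline is already collected, so the precision costs little.

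Protocol Section 3.5.4 treats daily urine volume as the measure of aquaretic effect on which OPC-61815 is compared with the tablet. With 10 to 11 subjects per arm those intervals will be wide. The stake is interval width on secondary endpoints that carry no decision rule. The sample size is justified only in terms of tolvaptan exposure, and the documents set no power or precision target for these contrasts.

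**Working it through.** The plan gives no precision figure for these contrasts, so there is nothing to reproduce beyond 5 × 10 = 50 evaluable and 5 × 11 = 55 treated.

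**Inputs.** n = 10 per arm (11 starting treatment), from SAP Section 4. The baseline-to-post correlation ρ and the SD ratio k = post-dose SD / baseline SD are assumed. The true slope on baseline is ρk.

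**Baseline imbalance.** The difference in baseline means between two arms has SD √(2/n) baseline SDs: √(2/10) = 0.447, √(2/11) = 0.426. A change score leaves only (1 − slope) of it. At n = 10 that is 0.36, 0.27, 0.18 and 0.09 at slopes 0.2, 0.4, 0.6 and 0.8.

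**Gain from a pairwise ANCOVA over a two-arm t on change.**
- Large-sample variance ratio: k²(1 − ρ²) / (1 + k² − 2ρk), which is (1 + ρ)/2 at k = 1.
- Small-sample factor for estimating the slope: 1 + 1/(df − 2), with df = 18, so 1 + 1/16 = 1.0625.
- One degree of freedom is lost: t(17)/t(18) = 2.1098/2.1009 = 1.0042.
- Width ratio: √(variance ratio × 1.0625) × 1.0042.

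With equal SDs (k = 1):

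| ρ | variance ratio | width ratio |
|---|---|---|
| 0.2 | 0.60 | 0.80 |
| 0.4 | 0.70 | 0.87 |
| 0.6 | 0.80 | 0.93 |
| 0.8 | 0.90 | 0.98 |

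Simulation of a five-arm ANCOVA with HC3 variance gave nearly the same: 0.801, 0.865, 0.926, 0.982.

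**Worst case against a two-arm t.** At slope 1 the variance ratio is 1, so the width ratio is √1.0625 × 1.0042 = 1.035. Simulation gave 1.034 (n = 10) and 1.030 (n = 11). Against a t interval pooled over five arms with common SDs, the loss at slope 1 is about 7%.

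**Sensitivity to the SD ratio.** Protocol Table 2.3-3 gives urine-volume SDs in healthy men. Taking a placebo SD as baseline and a dosed SD as post-dose:
- 951.5 and 861.8 (2 hours; 7.5 mg): 0.76, 0.82, 0.88, 0.93 at the four correlations.
- 951.5 and 1583.9 (2 hours; 15 mg): 0.96, 1.01, 1.03, 0.98. Here k = 1583.9/951.5 = 1.66, so ρ = 0.6 puts the slope at 1.00.
- 1412.2 and 614.1 (1 minute; 7.5 mg): 0.38 to 0.45.

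**Choice of variance.** In Protocol Table 2.3-2 urine-volume SD rises with OPC-61815 dose: 465.2, 756.2, 1213.4 and 1582.4, against 729.9 for the 15-mg tablet. These SDs were used for the post-dose values, with assumed baseline SDs of 750, 1000 and 1500 and correlations of 0.2, 0.5 and 0.8. That gives 3 × 3 × 4 = 36 comparisons at n = 10:
- Two-arm t on change: coverage about 94–95%.
- Pairwise ANCOVA, ordinary t: median width ratio 0.79 to the two-arm t, wider in 4 of 36 and by at most 3%; coverage about 93–97% across the runs made.
- Five-arm ANCOVA, HC3: median width ratio 0.81, wider in 6 of 36 and by up to about 10%; coverage 94.8–96.5%.
- Five-arm ANCOVA with one pooled variance: about 86–91% coverage for the highest-SD arm.
- Pooled five-arm t on change: 89.9–95.4% for that arm.

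**The case against.** The strongest reply is that nothing here is wrong. The contrast is unbiased, a two-arm t interval covers at its nominal level, and the endpoints are secondary. That stands, and it is why the point is optional.

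A reader might infer that the SAP contradicts itself by adjusting body weight but not urine volume. The documents do not support this: body weight, jugular venous distension and cardiothoracic ratio are efficacy endpoints, these three are pharmacodynamic, and protocol and SAP agree on leaving them unadjusted. Nor is chance baseline imbalance a bias. It averages to zero over randomization, and the change score already removes the share given by a slope of 1.

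A reader might also take the 0.38–0.45 ratios as a likely gain. They cannot bear that weight. The Table 2.3-3 pairs are separate groups of 5 or 6 healthy men, not baseline and post-dose values of the same people. By an F interval, the SD ratio for 1412.2 and 614.1 is 0.43 with 95% limits 0.16 to 1.33; for 951.5 and 1583.9 it is 1.66 with limits 0.62 to 4.45. None of those men had the 1-hour infusion, and no SD is given for fluid intake or balance.

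The dose-rising SDs belong to healthy adults at 3, 7.5, 15 and 30 mg, standing in for trial arms of 2, 4, 8 and 16 mg. They illustrate unequal variance and do not estimate it for this trial. Repeating the exercise with SDs from the nearest doses did not reverse the conclusion.

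Finally, a robust variance mainly repairs a problem that a five-arm model introduces. That is correct, and it favours the pairwise fit.

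**Conclusion.** The point holds as an optional improvement in efficiency. At equal SDs and 10 per arm, pairwise ANCOVA gives intervals about 20%, 13%, 7% and 2% narrower than a two-arm t at correlations 0.2, 0.4, 0.6 and 0.8. The downside is up to about 4% wider when the slope is near 1, or about 7% against a pooled t with common SDs. Against a pooled t the loss can be larger for the highest-SD arm when SDs rise with dose, but there the pooled t can itself under-cover.

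The size rests on assumed correlations and SDs and may differ between the three variables and between days. It would be too much to conclude that the planned results would be invalid or that the dose comparison on exposure is at risk: the primary Cmax and AUC24h analysis is separate. The one gap in specification is the unstated variance of the t interval.

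**What to change.** In SAP Section 11, for each OPC-61815 dose against the tablet on Day 1 and Day 5, fit an ANCOVA of change on arm with the same variable's 24-hour baseline as covariate. Use only the two arms compared and the ordinary t interval. Report the LS-mean difference with its two-sided 95% confidence interval. Keep raw mean changes, including the urine-volume bar graph (CF-5), as descriptive. Record the change in SAP Section 14, since it departs from Protocol Section 6.2.

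If one five-arm model is preferred, use an HC3 variance and not a single pooled one. If the sponsor keeps the unadjusted contrast, one clause stating that the t interval uses the two arms compared would close the specification gap.

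The cost is SAP wording and 3 variables × 2 days × 4 doses = 24 adjusted contrasts; Appendix 1 lists only descriptive tables for these variables (PDT-9 to PDT-11). No extra data are needed. HC3 would bring in a variance estimator that the SAP names nowhere else; the pairwise fit avoids that.

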Appendix 1**List of Tables and Figures**

CT-1	Subject Disposition (Screened Subjects)
CT-2.1	Reasons for Discontinuation (Randomized Subjects)
CT-2.2	Protocol Deviations (Randomized Subjects)
CT-3.1.1	Demographic and Baseline Characteristics (Safety Analysis Set)
CT-3.1.2	Demographic and Baseline Characteristics (Pharmacokinetics Analysis Set)
CT-3.1.3	Demographic and Baseline Characteristics (Pharmacokinetics Analysis Set (2))
CT-3.2.1	Medical History (1) (Safety Analysis Set)
CT-3.2.2	Medical History (1) (Pharmacokinetics Analysis Set)
CT-3.2.3	Medical History (1) (Pharmacokinetics Analysis Set (2))
CT-3.2.4	Medical History (2) (Safety Analysis Set)
CT-3.2.5	Medical History (2) (Pharmacokinetics Analysis Set)
CT-3.2.6	Medical History (2) (Pharmacokinetics Analysis Set (2))
CT-3.3.1	Concomitant Medications Used on the First Day of Trial Drug Administration (1) (Safety Analysis Set)
CT-3.3.2	Concomitant Medications Used on the First Day of Trial Drug Administration (1) (Pharmacokinetics Analysis Set)
CT-3.3.3	Concomitant Medications Used on the First Day of Trial Drug Administration (1) (Pharmacokinetics Analysis Set (2))
CT-3.3.4	Concomitant Medications Used on the First Day of Trial Drug Administration (2) (Safety Analysis Set)
CT-3.3.5	Concomitant Medications Used on the First Day of Trial Drug Administration (2) (Pharmacokinetics Analysis Set)
CT-3.3.6	Concomitant Medications Used on the First Day of Trial Drug Administration (2) (Pharmacokinetics Analysis Set (2))
CT-3.4.1	Baseline Disease Evaluation (Safety Analysis Set)
CT-3.4.2	Baseline Disease Evaluation (Pharmacokinetics Analysis Set)

CT-3.4.3 Baseline Disease Evaluation (Pharmacokinetics Analysis Set (2))

CT-5.1 Analysis of Covariance for Change from Baseline in Body Weight at Last Visit (Efficacy Analysis Set)

CT-5.2 Descriptive Statistics for Change from Baseline in Body Weight (Efficacy Analysis Set)

CT-5.3 Descriptive Statistics for Change Rate from Baseline in Body Weight (Efficacy Analysis Set)

CT-6.1.1 Improvement Rate for Lower Limb Edema and Pulmonary Congestion at Last Visit (Efficacy Analysis Set)

CT-6.1.2 Disappearance Rate for Lower Limb Edema and Pulmonary Congestion at Last Visit (Efficacy Analysis Set)

CT-6.2 Shift Table for Lower Limb Edema (Efficacy Analysis Set)

CT-6.3 Shift Table for Pulmonary Congestion (Efficacy Analysis Set)

CT-6.4 Analysis of Covariance for Change from Baseline in Juglar Venous Distension at Last Visit (Efficacy Analysis Set)

CT-6.5 Descriptive Statistics for Juglar Venous Distension (cm) (Efficacy Analysis Set)

CT-6.6 Analysis of Covariance for Change from Baseline in Cardiothoracic Ratio at Last Visit (Efficacy Analysis Set)

CT-6.7 Descriptive Statistics for Cardiothoracic Ratio (%) (Efficacy Analysis Set)

CT-6.8 Disappearance Rate for Pulmonary rales and Third Cardiac Sound at Last Visit (Efficacy Analysis Set)

CT-6.9 Shift Table for Pulmonary rales (Efficacy Analysis Set)

CT-6.10 Shift Table for Third Cardiac Sound (Efficacy Analysis Set)

CT-6.11 Shift Table for NYHA Classification (Efficacy Analysis Set)

CT-7.1 Extent of Exposure to Investigational Medicinal Product (Safety Analysis Set)

CT-7.2.1 Treatment Compliance (Safety Analysis Set)

CT-7.2.2 Treatment Compliance (Pharmacokinetics Analysis Set)

- CT-7.2.3 Treatment Compliance (Pharmacokinetics Analysis Set (2))
- CT-8.1 Overall Summary of Adverse Events (Safety Analysis Set)
- CT-8.2 Incidences of Treatment-emergent Adverse Events by MedDRA System Organ Class and Preferred Term (Safety Analysis Set)
- CT-8.3 Incidences of Potentially Drug-related Treatment-emergent Adverse Events by MedDRA System Organ Class and Preferred Term (Safety Analysis Set)
- CT-8.4 Incidences of Treatment-emergent Adverse Events by Severity by MedDRA System Organ Class and Preferred Term (Safety Analysis Set)
- CT-8.5 Incidences of Potentially Drug-related Treatment-emergent Adverse Events by Severity by MedDRA System Organ Class and Preferred Term (Safety Analysis Set)
- CT-8.6 Incidences of Treatment-emergent Adverse Events Greater Than or Equal to 2 Subjects in Any Treatment Group by MedDRA System Organ Class and Preferred Term (Safety Analysis Set)
- CT-8.7 Incidences of Potentially Drug-related Treatment-emergent Adverse Events Greater Than or Equal to 2 Subjects in Any Treatment Group by MedDRA System Organ Class and Preferred Term (Safety Analysis Set)
- CT-9.1 Incidences of Treatment-emergent Adverse Events with an outcome of death by MedDRA System Organ Class and Preferred Term (Safety Analysis Set)
- CT-9.2 Incidences of Potentially Drug-related Treatment-emergent Adverse Events with an outcome of death by MedDRA System Organ Class and Preferred Term (Safety Analysis Set)
- CT-9.3 Incidences of Serious Treatment-emergent Adverse Events by MedDRA System Organ Class and Preferred Term (Safety Analysis Set)
- CT-9.4 Incidences of Potentially Drug-related Serious Treatment-emergent Adverse Events by MedDRA System Organ Class and Preferred Term (Safety Analysis Set)
- CT-9.5 Incidences of Treatment-emergent Adverse Events Leading to Discontinuation of Investigational Medicinal Product Administration by MedDRA System Organ Class and Preferred Term (Safety Analysis Set)

CT-9.6 Incidences of Potentially Drug-related Treatment-emergent Adverse Events Leading to Discontinuation of Investigational Medicinal Product Administration by MedDRA System Organ Class and Preferred Term (Safety Analysis Set)

CT-9.7 Listing of Deaths (Safety Analysis Set)

CT-9.8 Listing of Subject With Serious Adverse Events Other Than Death (Safety Analysis Set)

CT-9.9 Listing of Subject With Adverse Events Leading to Discontinuation of Investigational Medicinal Product Administration (Safety Analysis Set)

CT-10.1.1 Mean Change from Baseline in Clinical Laboratory Test Results (Serum Chemistry) (Safety Analysis Set)

CT-10.1.2 Mean Change from Baseline in Clinical Laboratory Test Results (Hematology) (Safety Analysis Set)

CT-10.1.3 Mean Change from Baseline in Clinical Laboratory Test Results (Urinalysis) (Safety Analysis Set)

CT-10.2 Shift Tables of Clinical Laboratory Test Results (Qualitative Urinalysis) (Safety Analysis Set)

CT-10.3.1 Shift Tables of Clinical Laboratory Test Results (Serum Chemistry) (Safety Analysis Set)

CT-10.3.2 Shift Tables of Clinical Laboratory Test Results (NA, K) (Safety Analysis Set)

CT-10.3.3 Shift Tables of Clinical Laboratory Test Results (Hematology) (Safety Analysis Set)

CT-10.3.4 Shift Tables of Clinical Laboratory Test Results (Urinalysis) (Safety Analysis Set)

CT-10.4.1 Listing of Abnormal Laboratory Findings (Safety Analysis Set)

CT-10.4.2 Listing of Abnormal Laboratory Findings Potential Drug-Induced Liver Injury (Randomized Subjects)

CT-10.5 Incidence of Potential Drug-Induced Liver Injury (Safety Analysis Set)

CT-11 Mean Change from Baseline in Vital Signs (Safety Analysis Set)

CT-12.1 Mean Change from Baseline in Electrocardiogram Results (Safety Analysis Set)

CT-12.2 Shift Table of 12-Lead ECG Findings (Normal/Abnormal Assessments) (Safety Analysis Set)

CT-12.3.1 Incidence of Categorical Changes in Electrocardiogram Results in All Visits (Safety Analysis Set)

CT-12.3.2 Incidence of Categorical Changes in Electrocardiogram Results at Baseline (Run-in Period) (Safety Analysis Set)

CT-12.3.3 Incidence of Categorical Changes in Electrocardiogram Results on Day 1 (Safety Analysis Set)

CT-12.3.4 Incidence of Categorical Changes in Electrocardiogram Results on Day 3 (Safety Analysis Set)

CT-12.3.5 Incidence of Categorical Changes in Electrocardiogram Results on Day 6 (Safety Analysis Set)

CT-12.3.6 Incidence of Categorical Changes in Electrocardiogram Results on Last Visit (Safety Analysis Set)

PDT-1 Descriptive Statistics for Serum Sodium Concentration (mEq/L) (Pharmacodynamics Analysis Set)

PDT-2 Descriptive Statistics for Serum Potassium Concentration (mEq/L) (Pharmacodynamics Analysis Set)

PDT-3 Descriptive Statistics for Serum Osmolality (mOsm/kg) (Pharmacodynamics Analysis Set)

PDT-4 Descriptive Statistics for Plasma BNP Concentration (pg/mL) (Pharmacodynamics Analysis Set)

PDT-5 Descriptive Statistics for Serum pro BNP Concentration (pg/mL) (Pharmacodynamics Analysis Set)

PDT-6 Descriptive Statistics for Serum Troponin Concentration (pg/mL) (Pharmacodynamics Analysis Set)

PDT-7 Descriptive Statistics for Plasma AVP Concentration (pg/mL) (Pharmacodynamics Analysis Set)

PDT-8 Descriptive Statistics for Plasma Renin Activity (ng/mL/hr) (Pharmacodynamics Analysis Set)

PDT-9 Descriptive Statistics for Daily Urine Volume (mL) (Pharmacodynamics Analysis Set)

PDT-10 Descriptive Statistics for Daily Fluid Intake (mL) (Pharmacodynamics Analysis Set)

PDT-11 Descriptive Statistics for Daily Fluid Balance (mL) (Pharmacodynamics Analysis Set)

PDT-12 Descriptive Statistics for Daily Urine Excretion of Sodium (mEq) (Pharmacodynamics Analysis Set)

PDT-13 Descriptive Statistics for Daily Urine Excretion of Potassium (mEq) (Pharmacodynamics Analysis Set)

PDT-14 Descriptive Statistics for Urine Osmolality (mOsm/kg) (Pharmacodynamics Analysis Set)

CF-1 Transition Diagram for Body Weight (Efficacy Analysis Set)

CF-2 Bar Graph for Body Weight (Efficacy Analysis Set)

CF-3 Scatter Plot for Clinical Laboratory Tests (Safety Analysis Set)

CF-4 Transition Diagram for Daily Urine Volume (Pharmacodynamics Analysis Set)

CF-5 Bar Graph for Daily Urine Volume (Pharmacodynamics Analysis Set)

PKT-1.1.1.1 Individual and Summary of OPC-61815 Plasma Concentration Following Single Intravenous Administration of OPC-61815

PKT-1.1.1.2 Individual and Summary of OPC-41061 Plasma Concentration Following Single Intravenous Administration of OPC-61815

PKT-1.1.1.3 Individual and Summary of DM-4103 Plasma Concentration Following Single Intravenous Administration of OPC-61815

PKT-1.1.1.4 Individual and Summary of DM-4107 Plasma Concentration Following Single Intravenous Administration of OPC-61815

PKT-1.1.2.1 Individual and Summary of OPC-61815 Plasma Pharmacokinetic Parameters Following Single Intravenous Administration of OPC-61815

PKT-1.1.2.2 Individual and Summary of OPC-41061 Plasma Pharmacokinetic Parameters Following Single Intravenous Administration of OPC-61815

- PKT-1.1.2.3 Individual and Summary of DM-4103 Plasma Pharmacokinetic Parameters Following Single Intravenous Administration of OPC-61815
- PKT-1.1.2.4 Individual and Summary of DM-4107 Plasma Pharmacokinetic Parameters Following Single Intravenous Administration of OPC-61815
- PKT-1.1.3.1 Individual and Summary of OPC-61815 Plasma Concentration Following Multiple Intravenous Administration of OPC-61815
- PKT-1.1.3.2 Individual and Summary of OPC-41061 Plasma Concentration Following Multiple Intravenous Administration of OPC-61815
- PKT-1.1.3.3 Individual and Summary of DM-4103 Plasma Concentration Following Multiple Intravenous Administration of OPC-61815
- PKT-1.1.3.4 Individual and Summary of DM-4107 Plasma Concentration Following Multiple Intravenous Administration of OPC-61815
- PKT-1.1.4.1 Individual and Summary of OPC-61815 Plasma Trough Concentration Following Intravenous Administration of OPC-61815
- PKT-1.1.4.2 Individual and Summary of OPC-41061 Plasma Trough Concentration Following Intravenous Administration of OPC-61815
- PKT-1.1.4.3 Individual and Summary of DM-4103 Plasma Trough Concentration Following Intravenous Administration of OPC-61815
- PKT-1.1.4.4 Individual and Summary of DM-4107 Plasma Trough Concentration Following Intravenous Administration of OPC-61815
- PKT-1.1.6.1 Individual and Summary of OPC-61815 Plasma Accumulation Parameters Following Multiple Intravenous Administration of OPC-61815
- PKT-1.1.6.2 Individual and Summary of OPC-41061 Plasma Accumulation Parameters Following Multiple Intravenous Administration of OPC-61815
- PKT-1.1.6.3 Individual and Summary of DM-4103 Plasma Accumulation Parameters Following Multiple Intravenous Administration of OPC-61815
- PKT-1.1.6.4 Individual and Summary of DM-4107 Plasma Accumulation Parameters Following Multiple Intravenous Administration of OPC-61815
- PKT-1.2.1.1 Individual and Summary of OPC-41061 Plasma Concentration Following Single Oral Administration of OPC-41061

- PKT-1.2.1.2 Individual and Summary of OPC-61815 Plasma Concentration Following Single Oral Administration of OPC-41061
- PKT-1.2.1.3 Individual and Summary of DM-4103 Plasma Concentration Following Single Oral Administration of OPC-41061
- PKT-1.2.1.4 Individual and Summary of DM-4107 Plasma Concentration Following Single Oral Administration of OPC-41061
- PKT-1.2.2.1 Individual and Summary of OPC-41061 Plasma Pharmacokinetic Parameters Following Single Oral Administration of OPC-41061
- PKT-1.2.2.2 Individual and Summary of OPC-61815 Plasma Pharmacokinetic Parameters Following Single Oral Administration of OPC-41061
- PKT-1.2.2.3 Individual and Summary of DM-4103 Plasma Pharmacokinetic Parameters Following Single Oral Administration of OPC-41061
- PKT-1.2.2.4 Individual and Summary of DM-4107 Plasma Pharmacokinetic Parameters Following Single Oral Administration of OPC-41061
- PKT-1.2.3.1 Individual and Summary of OPC-41061 Plasma Concentration Following Multiple Intravenous Administration of OPC-41061
- PKT-1.2.3.2 Individual and Summary of OPC-61815 Plasma Concentration Following Multiple Intravenous Administration of OPC-41061
- PKT-1.2.3.3 Individual and Summary of DM-4103 Plasma Concentration Following Multiple Intravenous Administration of OPC-41061
- PKT-1.2.3.4 Individual and Summary of DM-4107 Plasma Concentration Following Multiple Intravenous Administration of OPC-41061
- PKT-1.2.4.1 Individual and Summary of OPC-41061 Plasma Trough Concentration Following Oral Administration of OPC-41061
- PKT-1.2.4.2 Individual and Summary of OPC-61815 Plasma Trough Concentration Following Oral Administration of OPC-41061
- PKT-1.2.4.3 Individual and Summary of DM-4103 Plasma Trough Concentration Following Oral Administration of OPC-41061
- PKT-1.2.4.4 Individual and Summary of DM-4107 Plasma Trough Concentration Following Oral Administration of OPC-41061
- PKT-1.2.6.1 Individual and Summary of OPC-41061 Plasma Accumulation Parameters Following Multiple Oral Administration of OPC-41061

- PKT-1.2.6.2 Individual and Summary of OPC-61815 Plasma Accumulation Parameters Following Multiple Oral Administration of OPC-41061
- PKT-1.2.6.3 Individual and Summary of DM-4103 Plasma Accumulation Parameters Following Multiple Oral Administration of OPC-41061
- PKT-1.2.6.4 Individual and Summary of DM-4107 Plasma Accumulation Parameters Following Multiple Oral Administration of OPC-41061
- PKT-1.3.1.1 Comparison of OPC-41061 Exposure (Cmax and AUC24h) Between Single Intravenous Administration of OPC-61815 and Single Oral Administration of OPC-41061
- PKF-1.1.1.1 Mean OPC-61815 Plasma Concentrations Following Single Intravenous Administration of OPC-61815
- PKF-1.1.1.2 Mean OPC-41061 Plasma Concentrations Following Single Intravenous Administration of OPC-61815
- PKF-1.1.1.3 Mean DM-4103 Plasma Concentrations Following Single Intravenous Administration of OPC-61815
- PKF-1.1.1.4 Mean DM-4107 Plasma Concentrations Following Single Intravenous Administration of OPC-61815
- PKF-1.1.2.1 Median OPC-61815 Plasma Concentrations Following Single Intravenous Administration of OPC-61815
- PKF-1.1.2.2 Median OPC-41061 Plasma Concentrations Following Single Intravenous Administration of OPC-61815
- PKF-1.1.2.3 Median DM-4103 Plasma Concentrations Following Single Intravenous Administration of OPC-61815
- PKF-1.1.2.4 Median DM-4107 Plasma Concentrations Following Single Intravenous Administration of OPC-61815
- PKF-1.1.3.1 OPC-61815 Plasma Concentrations Following Single Intravenous Administration of OPC-61815
- PKF-1.1.3.2 OPC-41061 Plasma Concentrations Following Single Intravenous Administration of OPC-61815
- PKF-1.1.3.3 DM-4103 Plasma Concentrations Following Single Intravenous Administration of OPC-61815

- PKF-1.1.3.4 DM-4107 Plasma Concentrations Following Single Intravenous Administration of OPC-61815
- PKF-1.1.4.1 Mean OPC-61815 Plasma Concentrations Following Multiple Intravenous Administration of OPC-61815
- PKF-1.1.4.2 Mean OPC-41061 Plasma Concentrations Following Multiple Intravenous Administration of OPC-61815
- PKF-1.1.4.3 Mean DM-4103 Plasma Concentrations Following Multiple Intravenous Administration of OPC-61815
- PKF-1.1.4.4 Mean DM-4107 Plasma Concentrations Following Multiple Intravenous Administration of OPC-61815
- PKF-1.1.5.1 Median OPC-61815 Plasma Concentrations Following Multiple Intravenous Administration of OPC-61815
- PKF-1.1.5.2 Median OPC-41061 Plasma Concentrations Following Multiple Intravenous Administration of OPC-61815
- PKF-1.1.5.3 Median DM-4103 Plasma Concentrations Following Multiple Intravenous Administration of OPC-61815
- PKF-1.1.5.4 Median DM-4107 Plasma Concentrations Following Multiple Intravenous Administration of OPC-61815
- PKF-1.1.6.1 Mean OPC-61815 Plasma Trough Concentrations Following Intravenous Administration of OPC-61815
- PKF-1.1.6.2 Mean OPC-41061 Plasma Trough Concentrations Following Intravenous Administration of OPC-61815
- PKF-1.1.6.3 Mean DM-4103 Plasma Trough Concentrations Following Intravenous Administration of OPC-61815
- PKF-1.1.6.4 Mean DM-4107 Plasma Trough Concentrations Following Intravenous Administration of OPC-61815
- PKF-1.1.7.1 Median OPC-61815 Plasma Trough Concentrations Following Intravenous Administration of OPC-61815
- PKF-1.1.7.2 Median OPC-41061 Plasma Trough Concentrations Following Intravenous Administration of OPC-61815
- PKF-1.1.7.3 Median DM-4103 Plasma Trough Concentrations Following Intravenous Administration of OPC-61815

- PKF-1.1.7.4 Median DM-4107 Plasma Trough Concentrations Following Intravenous Administration of OPC-61815
- PKF-1.1.8.1 Mean OPC-61815 Plasma Concentrations Following Single and Multiple Intravenous Administration of OPC-61815
- PKF-1.1.8.2 Mean OPC-41061 Plasma Concentrations Following Single and Multiple Intravenous Administration of OPC-61815
- PKF-1.1.8.3 Mean DM-4103 Plasma Concentrations Following Single and Multiple Intravenous Administration of OPC-61815
- PKF-1.1.8.4 Mean DM-4107 Plasma Concentrations Following Single and Multiple Intravenous Administration of OPC-61815
- PKF-1.1.9.1 Median OPC-61815 Plasma Concentrations Following Single and Multiple Intravenous Administration of OPC-61815
- PKF-1.1.9.2 Median OPC-41061 Plasma Concentrations Following Single and Multiple Intravenous Administration of OPC-61815
- PKF-1.1.9.3 Median DM-4103 Plasma Concentrations Following Single and Multiple Intravenous Administration of OPC-61815
- PKF-1.1.9.4 Median DM-4107 Plasma Concentrations Following Single and Multiple Intravenous Administration of OPC-61815
- PKF-1.1.10.1 OPC-61815 Plasma Concentrations Following Multiple Intravenous Administration of OPC-61815
- PKF-1.1.10.2 OPC-41061 Plasma Concentrations Following Multiple Intravenous Administration of OPC-61815
- PKF-1.1.10.3 DM-4103 Plasma Concentrations Following Multiple Intravenous Administration of OPC-61815
- PKF-1.1.10.4 DM-4107 Plasma Concentrations Following Multiple Intravenous Administration of OPC-61815
- PKF-1.1.11.1 OPC-61815 Plasma Trough Concentrations Following Intravenous Administration of OPC-61815
- PKF-1.1.11.2 OPC-41061 Plasma Trough Concentrations Following Intravenous Administration of OPC-61815
